5.4. Dose Justification

5.4.1. Starting dose for Part A

[figure not shown]
Inhibition of KMO in pre-clinical species results not only in a decrease in the rate of formation of 3HK, but also in an accumulation of KYN. This increase in KYN works to oppose the inhibition of KMO by increasing flux through the pathway. In rats, the maximal steady state change in KYN observed following KMO inhibition was between 6 and 10-fold, while in mice deficient in KMO the baseline KYN level was 19 times higher than in wild type animals (Mole et al, 2016). The magnitude of increase in KYN that will be observed in humans is not known so it is not possible to predict exactly what level of 3HK reduction will be observed at any given drug level. Instead modelling has been used to establish an appropriate dose range to cover a range of potential human scenarios (2 fold to 20-fold increase in KYN).

A model was developed to simulate the clinical doses according to the range increase in KYN previously mentioned and for different degrees of 3HK inhibition. The model utilised the PK preclinical parameters that were scaled to the human counterparts. More specifically, the volume of distribution (V) was predicted from the mean of rat and dog volumes, giving a value of 0.39 L/kg (27 L). Prediction of human clearance (CL) was undertaken using scaling from rat and dog with the method of exponents. Similar values were obtained using methods either restricted (2.9 L/hr) or non restricted (1.9 L/hr) by plasma protein binding so subsequent dose estimates use the mean of these values (2.4 L/hr). Finally, the half-life is predicted to be 7.8 h.

To set the starting dose minimum anticipated biological effect level (MABEL), it was first assumed that the magnitude of the maximal KYN change observed in man following KMO inhibition will be substantially smaller than in the rat (2 fold compared to 6-10 fold), thus making the pathway more sensitive to inhibition. Under these circumstances, a dose targeting 0.2 times the cellular Ki would decrease 3HK levels by no more than 10-20 % while having no measurable impact on KYN levels. In contrast, if the magnitude of the maximal change in KYN in man is assumed to be substantially higher than in the rat (20 fold compared 6-10 fold), then a dose targeting 0.2 times the cellular Ki would be predicted to have no measurable effect on either 3HK or KYN levels. This has therefore

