been selected as the MABEL dose. The figure below depicts the predicted PK profile for the MABEL dose.

In accordance with FDA guidance, the maximum recommended starting dose (MRSD) is 1/10th (applying the default safety factor) the NOAEL human equivalent dose (HED) in the more sensitive or more relevant preclinical species, correcting for body surface area between species. For GSK3335065 the more sensitive species is the rat as in the rat the lowest HED can be identified. The safety factor may be adjusted depending on the expected pharmacology, toxicology, and preclinical pharmacokinetics of the drug candidate, or previous experience with compounds in the same pharmacologic/structural class. As this is a novel mechanism a more conservative safety factor of 100 to calculate the MRSD was used.

Using the data from the 2 week Good laboratory practices (GLP) toxicity studies in rat, the MRSD was estimated to be 16 mg based on the following calculations:

$140 \text{ mg/kg/day} / 6.2 = 22.6 \text{ mg/kg} / 100 = 0.226 \text{ mg/kg}$; for a 70 kg human the MRSD is ~ 16mg. Hence, the proposed 0.1 mg MABEL starting dose is approximately 160-fold below the MRSD of 16 mg.

The planned doses and predicted exposures compared to the 2 week GLP study in rats are shown in [Table 9](#) below.

Table 9 Part A Planned doses, predicted exposures, and anticipated margins to rat NOAELs

	Dose	Predicted Cmax (fold Ki) (μ g/ml)	Margin to NOAEL (Cmax)	Predicted AUC (0-24h) (μ g.hr.mL ⁻¹)	Margin to NOAEL (AUC 0-24h)
Cohort 1, Period 1	0.1 mg IV bolus	0.004 (0.2xKi)	39750	0.036	46667
Cohort 2, Period 1	0.25 mg IV bolus	0.01 (1xKi)	15900	0.091	18462
To facilitate subject recruitment, the study design will be changed to a parallel cohort design (Amendment 3).					
Cohort 3	1.3 mg IV bolus	0.05 (5xKi)	3180	0.481	3493
Cohort 4	2.6 mg IV bolus	0.1 (10xKi)	1590	0.944	1780
Cohort 5	5.5 mg IV bolus	0.2 (20xKi)	795	2.020	832
Cohort 6	12 mg IV bolus	0.46 (50xKi)	346	4.398	382
Cohort 7	35 mg IV bolus	1.37 (150xKi)	116	12.753	132
Cohort 8	54 mg IV bolus	2.0 (220xKi)	80	22.4	75

Dose Escalation Approach in Part A

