The highest dose planned in Part A is a 54 mg dose with an expected exposure margin in terms of AUC to the rat NOAEL of 75-fold. Higher doses may be administered if exposures are lower than predicted but the maximum exposure will not exceed the 75-fold exposure margin in terms of AUC to the rat NOAEL.

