5.4.3. Maximum dose/exposure in Part B

The highest dose planned to be explored will target a concentration just over 100 times the Ki in PART B. Modelling suggests that the highest anticipated dose (73.4 mg total dose on day 1 followed by 50.4 mg/day on days 2-7) should achieve reductions of 3HK in excess of 90% even if the increase in KYN observed is substantially larger than that seen in the rat (20 fold compared to 6-10 fold). This value remains below (177-fold for Cmax and 75-fold for AUC(0-24h)) the plasma concentration at the NOAEL in the toxicity studies in rats and dogs. The highest dose also remains below the threshold for increased drug induced liver injury (DILI) risk (100 mg). Higher doses may be administered if exposures are lower than predicted but the maximum exposure will not exceed the 75-fold exposure margin in terms of AUC to the NOAEL.

This dose is anticipated to reduce 3HK levels by >90%. Preclinical data support that lowering 3HK levels through KMO inhibition >90% in humans is anticipated to be safe as KMO deficient mice have undetectable levels of 3HK and elevation of metabolites, such as kynureneine (KYN), kynurenic acid (KYNA) and anthranilic acid (AA), but appear viable and healthy. A robust decrease in 3HK of >90% was observed in the dog 7-day dose range finding study. 3HK levels could not be determined in the rat study. However the mid dose used in this rat study had previously been shown to reduce 3HK levels by ~85% on the first day of dosing in a pharmacology study. Any adverse effects of changes in 3HK would have been noted in these studies.

Table 10 Part B planned doses, predicted exposures, and anticipated margins to rat NOAEL. 4 ascending doses are planned in Part B.

	Dose range IVB & IV infusion	Expected (%) KMO inhibition	Targeted Concentration (Cmax) (ug/ml)	Margin to NOAEL (Cmax)	AUC(0-168h) (ug.hr.mL ⁻¹)	Margin to NOAEL (AUC 0-24h)
Anticipated starting dose	IVB 0.14 mg + IV Inf. 0.012 mg/h	25%	0.005 (0.6xKi)	31800	0.9	13067
Anticipated pharmacologically active dose	IVB 7.5 mg + IV Inf. 0.63 mg/h	>60%	0.27 (30xKi)	589	47	250
Anticipated pharmacologically active dose	IVB 12 mg + IV Inf. 1.1 mg/h	>85%	0.45 (50xKi)	353	85	138
Highest anticipated dose	IVB 23 mg + IV Inf. 2.1 mg/h	>90%	0.9 (100xKi)	177	156	75

5.4.4. Part C:

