7.2. Dose Modification

In case a dose reduction is necessary, the study treatment will be administered as follows:

- This protocol allows some alteration from the currently outlined dosing schedule, but the maximum predicted exposures will not exceed the 75-fold exposure margin in terms of AUC to the rat NOAEL as defined in the 14-day preclinical GLP tox studies.
- The decision to proceed to the next dose level of GSK3335065, will be made by the GSK Study Team based on safety, tolerability and available pharmacokinetic and/or pharmacodynamic data obtained in at least 6 subjects on GSK3335065 at the prior dose level. The actual doses to be administered may be adjusted based on safety, tolerability and preliminary pharmacokinetic and/or pharmacodynamic data at previous dose levels; these dose adjustments may involve either an increase or a decrease in the planned dose.
- The dosing schedule may also be adjusted to expand a dosing cohort to further evaluate safety, tolerability, pharmacokinetic and/or pharmacodynamic findings at a given dose level, or to add cohorts to evaluate additional dose levels. The study procedures for these additional subject(s) or cohort(s) will be the same as that described for other study subjects.
- If the same Serious Adverse Event (SAE) occurs in more than one subject, the dose escalation will be temporarily halted and no further subject will be dosed until a full safety review of the data has taken place. Relevant reporting and discussion with the Medical Monitor, relevant GSK personnel, and with the Ethics Committee will then take place prior to any resumption of dosing.
- The above criteria will apply even if measured pharmacokinetic parameters are below the above mentioned PK stopping criteria, and every effort will be made to take a blood sample at the time of the event for pharmacokinetic analysis in the presence of any of the above events.

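### The 54 mg ceiling row of Table 9 does not fit its AUC(0-24h) label, Table 10 mixes AUC intervals, and the 75-fold limit is stated without an interval

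*Protocol*

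**What the plan says.** Protocol section 5.4.1 predicts human kinetics from rat and dog: clearance 2.4 L/h, volume 27 L, and "the half-life is predicted to be 7.8 h". Table 9 uses them to predict exposure at eight bolus doses. Its exposure column has one label for every row ("Predicted AUC (0-24h"), and the last row reads "54 mg IV bolus 2.0 (220xKi) 80 22.4 75", so AUC is 22.4 and the AUC margin is 75.

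The same section describes the top planned dose as "a 54 mg dose with an expected exposure margin in terms of AUC to the rat NOAEL of 75-fold". It allows higher doses if exposure turns out lower than predicted, provided the 75-fold margin is kept. Section 7.2 repeats the constraint: "the maximum predicted exposures will not exceed the 75-fold exposure margin in terms of AUC to the rat NOAEL". Similar wording stands in 5.1.1, 5.4.3 and Appendix 3. None of these limit sentences gives an AUC interval.

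In section 5.4.3, Table 10 labels Part B exposure as AUC(0-168h), but its margin column is headed "Margin to NOAEL (AUC 0-24h"). The text of that section describes the top Part B regimen as 75-fold on AUC(0-24h).

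**The concern.** The 75-fold margin is the planned ceiling on exposure in Parts A and B, and it is the test for going above the tabulated doses. A ceiling of this kind needs one defined quantity. Here the row that illustrates the Part A ceiling departs from its column, the Part B table carries two intervals, and the rule itself names none.

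The choice of interval became more important once data arrived. Section 5.4.1 (Preliminary PK Data) reports that 24-hour exposure in Cohorts 1 and 2 agreed broadly with prediction, while the half-life was much longer than predicted. Section 9.3 puts it at about 35 h. When more of the exposure falls after 24 h, a margin on AUC(0-24h) and a margin on total AUC move apart. In addition, the planned PK parameters (Protocol sections 4 and 10.3.6) are AUC(0-t) and AUC to infinity. AUC(0-24h), the interval on the margin columns, is not listed.

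**Working it through.** **Inputs.** CL = 2.4 L/h and V = 27 L (Protocol 5.4.1). Elimination rate k = 2.4/27 = 0.0889 per h, so half-life = ln 2/0.0889 = 7.8 h, which matches the protocol. The rat NOAEL AUC is not stated. Multiplying margin by AUC in Table 9 gives 1680.0 to 1683.4 across all eight rows, so 1680 is used.

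**Table 9.** For a one-compartment bolus, AUC(0-24h) = (dose/CL) × (1 − e^(−24k)) = (dose/CL) × 0.8816, and AUC to infinity = dose/CL.

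| Dose (mg) | Stated AUC | AUC(0-24h) | Dose/CL | Stated AUC per mg |
|---|---|---|---|---|
| 0.1 | 0.036 | 0.0367 | 0.0417 | 0.360 |
| 0.25 | 0.091 | 0.0918 | 0.104 | 0.364 |
| 1.3 | 0.481 | 0.478 | 0.542 | 0.370 |
| 2.6 | 0.944 | 0.955 | 1.083 | 0.363 |
| 5.5 | 2.020 | 2.020 | 2.292 | 0.367 |
| 12 | 4.398 | 4.408 | 5.000 | 0.367 |
| 35 | 12.753 | 12.86 | 14.58 | 0.364 |
| 54 | 22.4 | 19.8 | 22.5 | 0.415 |

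The first seven rows reproduce as AUC(0-24h) within about 2%; dose/CL overshoots them by 13 to 16%. The 54 mg row does the opposite: AUC(0-24h) is 11.5% below the printed figure and dose/CL is within 0.4% of it. A check that needs no model is to scale the 35 mg row: 12.753 × 54/35 = 19.7. The margin on the labelled interval is 1680/19.8 = 85 (1680/19.7 = 85). Note also that 1680/75 = 22.4 exactly.

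**Table 10.** Bolus B plus infusion rate R over 168 h: AUC(0-168h) = (B/CL)(1 − e^(−168k)) + (R/CL)[168 − (1 − e^(−168k))/k], and total dose/CL = (B + 168R)/CL. For 23 mg + 2.1 mg/h the first is 9.58 + 0.875 × 156.75 = 146.7 and the second is 375.8/2.4 = 156.6.

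| Regimen | Stated AUC | Total dose/CL | AUC(0-168h) | 7 × 1680/stated AUC | Stated margin |
|---|---|---|---|---|---|
| 0.14 mg + 0.012 mg/h | 0.9 | 0.898 | 0.842 | 13067 | 13067 |
| 7.5 mg + 0.63 mg/h | 47 | 47.2 | 44.3 | 250 | 250 |
| 12 mg + 1.1 mg/h | 85 | 82.0 | 76.8 | 138 | 138 |
| 23 mg + 2.1 mg/h | 156 | 156.6 | 146.7 | 75 | 75 |

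Every margin is seven times 1680 divided by the stated AUC, that is, a margin on one-seventh of the course AUC. The 7.5 mg and 23 mg rows match total dose/CL, not AUC(0-168h). With CL held at 2.4 and the displayed doses and rates (and V) varied within rounding, AUC(0-168h) reaches at most 44.7 and 150.4 in those rows. On the labelled AUC(0-168h) the top-row margin is 11760/146.7 = 80. On day-1 AUC(0-24h) it is 1680/20.8 = 81.

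**Effect of half-life.** The share of a bolus AUC that falls in 0-24 h is 1 − 2^(−24/half-life). It is 0.88 at 7.8 h and 0.38 at 35 h if decline is mono-exponential. The ratio of total AUC to AUC(0-24h) is then 1/0.88 = 1.1 to 1/0.38 = 2.6.

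**The case against.** The best reply is that the interval can be inferred. Wherever the protocol attaches an interval to a NOAEL margin it is 0-24h: the margin columns of Tables 9 and 10, and the text of 5.4.3 on the top Part B regimen. No sentence expresses the limit on AUC to infinity. This stands, and it narrows the gap to limit sentences that lack an interval plus tables that do not follow the one implied.

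The reply is also right about direction. On predicted kinetics the labelled interval gives wider margins than those printed, about 85 in Part A and 80 in Part B. The tabulated doses are described as provisional, Part B was to be reviewed against Part A data before starting, and the SAP introduction records that the study ended after sentinel dosing in Cohort 3. That cohort's dose was 1.3 mg, where Table 9 gives a margin of 3493, so neither ceiling was approached.

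Four stronger readings are tempting, and the documents do not support them:

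- **That the 54 mg row is AUC to infinity.** It agrees with dose/CL, but it is also exactly 1680/75, so it may have been solved back from the limit. The protocol does not say how it was obtained.
- **That two readings of the limit are 2.6-fold apart.** That is the extreme of an illustrative range. Keeping V at 27 L with a 35 h half-life gives CL = 0.693 × 27/35 = 0.53 L/h and AUC(0-24h) of 0.378/0.535 = 0.71 per mg. This is about 1.9 times the predicted 0.367 and does not fit the report that 24-hour exposure was near prediction. A multiphasic profile would put the 24-hour share above 38%.
- **That the 12 mg + 1.1 mg/h row is an error.** Total dose/CL gives 82 against 85, but rounding of the displayed dose and rate spans 78.3 to 85.7. Table 3 does build its totals from the displayed values, so rounding is not proven either.
- **That all of Table 10 is total dose/CL.** Only two rows show it clearly; the lowest row is too coarsely rounded to tell.

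**Conclusion.** The point holds as an inconsistency in the plan. The 54 mg row overstates AUC(0-24h) by about 13% (22.4 against 19.8), so its margin on the labelled interval is about 85, not 75. Table 10 pairs a 0-168h exposure with a 0-24h margin, and in two rows the exposure is total dose/CL, about 6 to 7% above AUC(0-168h). The limit sentences name no interval, though the surrounding text favours 0-24h.

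A reader might infer that the planned doses breach the limit. The documents do not show that: on predicted kinetics the discrepancy is conservative. The reason to resolve it is that the longer observed half-life makes the interval matter, by a factor somewhere between about 1.1 and 2.6.

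This rests on the one-compartment model implied by the stated CL, V and half-life, on a NOAEL AUC of about 1680 inferred from the tables, and, for the upper end of that range, on mono-exponential decline at 35 h. The finding on the 54 mg row is firm, because scaling from the 35 mg row shows it without a model. The account of how Table 10 was built is less certain.

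**What to change.** State which AUC interval defines the 75-fold limit, and use it wherever the limit appears: Protocol 5.1.1, 5.4.1, 5.4.3, 7.2 and Appendix 3. Give the rat NOAEL AUC and its interval beside the tables, so that the margins can be checked. Reconcile the 54 mg row of Table 9 and the AUC and margin columns of Table 10 to the chosen interval. If that interval is AUC(0-24h), the other seven rows of Table 9 can stand, and AUC(0-24h) should be added to the planned PK parameters. The choice of interval, limit and doses belongs to the sponsor; the passages only need to agree.

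The cost is a short recalculation and wording in five places, with no new data. As dosing has ended, a correcting note in the study report would serve.

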5.4.2. Starting dose for Part B

Prior to initiation of Part B a review of all available safety, tolerability, PK and PD data from Part A will be conducted and potential changes to the dosing paradigm, safety observation period and assessments will be communicated in a future amendment to the protocol as appropriate.

In addition to safety/tolerability and PK, the goal of Part B is to characterize the dose-response relationship on KMO inhibition using 4 ascending doses.

Dosing in Part A will be completed prior to initiation of dosing in Part B. The first dose level in Part B will be set to ensure that the highest exposures safely achieved in Part A are not expected to be exceeded. The final decision on the starting dose in Part B will be made after review of preliminary Part A safety, tolerability, PK and PD data. A potential starting dose in Part B could be 0.14 mg IVB + 0.012 mg/h continuous infusion (predicted AUC(0-168) 0.9 ug.hr.ml⁻¹ correlating with an anticipated KMO inhibition of approximately 25%). Based on current predictions a 5.5 mg single dose (Panel 5) is expected to result in an exposure of ~2 ug.hr.ml⁻¹ (AUC 0-24h) providing sufficient PK coverage for a 0.14mg IVB + 0.012 mg/h continuous infusion dose over 7 days.

Dose Escalation Approach in Part B

In Part B, a decision to proceed to the next dose level will be based on data obtained up to 15 days post dose (discharge from clinical unit) from at least 6 subjects at the prior dose level. The review data set will at a minimum consist of the listings of any adverse events, flagged vital signs, flagged findings during the neuropsychiatric testing, flagged findings during the cardiac monitoring (telemetry) ECG, 12-lead ECGs, laboratory findings (including LFTs, cTN, BNP), and available PK and PD (3HK levels as PD BMx) data. Doses will be selected to ensure a complete coverage of the range of pharmacological effects based on data observed in Part A as is possible based on acceptable safety and tolerability. As a guide the doses (i.v. bolus and infusion rates) to achieve the clinical

concentrations within the minimal and maximal targeted concentrations were estimated to be per as [Table 10](#) below.

Anticipated Clinically Efficacious Dose

The PK/PD study conducted in rats suggests that a concentration around 20 times the cellular Ki would be required to achieve an 85% decrease in 3HK levels. GSK3335065 has cellular half maximal potency around 3 nM giving an apparent cellular Ki of 0.85 nM. It is largely excluded from erythrocytes, giving a blood:plasma ratio in human blood of 0.62, and is moderately bound by human plasma proteins, with a free fraction of 2.0% at 10 μ M. Thus the minimal level required to achieve 85% inhibition would be a free drug level of 17 nM, requiring total plasma drug level of 850 nM or total blood drug levels of 525 nM (0.18 ug/mL).

5.4.3. Maximum dose/exposure in Part B

The highest dose planned to be explored will target a concentration just over 100 times the Ki in PART B. Modelling suggests that the highest anticipated dose (73.4 mg total dose on day 1 followed by 50.4 mg/day on days 2-7) should achieve reductions of 3HK in excess of 90% even if the increase in KYN observed is substantially larger than that seen in the rat (20 fold compared to 6-10 fold). This value remains below (177-fold for Cmax and 75-fold for AUC(0-24h)) the plasma concentration at the NOAEL in the toxicity studies in rats and dogs. The highest dose also remains below the threshold for increased drug induced liver injury (DILI) risk (100 mg). Higher doses may be administered if exposures are lower than predicted but the maximum exposure will not exceed the 75-fold exposure margin in terms of AUC to the NOAEL.

This dose is anticipated to reduce 3HK levels by >90%. Preclinical data support that lowering 3HK levels through KMO inhibition >90% in humans is anticipated to be safe as KMO deficient mice have undetectable levels of 3HK and elevation of metabolites, such as kynureneine (KYN), kynurenic acid (KYNA) and anthranilic acid (AA), but appear viable and healthy. A robust decrease in 3HK of >90% was observed in the dog 7-day dose range finding study. 3HK levels could not be determined in the rat study. However the mid dose used in this rat study had previously been shown to reduce 3HK levels by ~85% on the first day of dosing in a pharmacology study. Any adverse effects of changes in 3HK would have been noted in these studies.

Table 10 Part B planned doses, predicted exposures, and anticipated margins to rat NOAEL. 4 ascending doses are planned in Part B.

	Dose range IVB & IV infusion	Expected (%) KMO inhibition	Targeted Concentration (Cmax) (ug/ml)	Margin to NOAEL (Cmax)	AUC(0-168h) (ug.hr.mL ⁻¹)	Margin to NOAEL (AUC 0-24h)
Anticipated starting dose	IVB 0.14 mg + IV Inf. 0.012 mg/h	25%	0.005 (0.6xKi)	31800	0.9	13067
Anticipated pharmacologically active dose	IVB 7.5 mg + IV Inf. 0.63 mg/h	>60%	0.27 (30xKi)	589	47	250
Anticipated pharmacologically active dose	IVB 12 mg + IV Inf. 1.1 mg/h	>85%	0.45 (50xKi)	353	85	138
Highest anticipated dose	IVB 23 mg + IV Inf. 2.1 mg/h	>90%	0.9 (100xKi)	177	156	75

5.4.4. Part C:

Doses selected for Part C (single or repeated administration) will be based on doses shown to be safe and tolerable in Parts A and B respectively and is expected to sit in the pharmacologically relevant range.

6. STUDY POPULATION

Prospective approval of protocol deviations to recruitment and enrollment criteria, also known as protocol waivers or exemptions, is not permitted.

6.1. Inclusion Criteria

Participants are eligible to be included in the study only if all of the following criteria apply:

Age

1. Participant must be 18 to 50 years of age inclusive, at the time of signing the informed consent. In Part C (WONCBP) participants must be between 18 and 60 years of age.

Type of Participant and Disease Characteristics

2. Participants who are overtly healthy as determined by medical evaluation including medical history, physical examination, laboratory tests, and cardiac monitoring.
3. A subject with a clinical abnormality or laboratory parameter(s) which is/are not specifically listed in the inclusion or exclusion criteria, outside the reference range for the population being studied may be included only if the investigator in consultation with the Medical Monitor if required agree and document that the finding is unlikely to introduce additional risk factors and will not interfere with the study procedures.

Weight

4. Body weight >50kg and body mass index (BMI) within the range 18.5 – 32 kg/m² (inclusive).

Sex

5. Abstinence/contraceptives: Length of time required for abstinence or use of contraceptives should take into account the reproductive toxicity profile including genotoxicity and teratogenicity, the size of the molecule, and the number of doses.

a. Male participants:

A male participant must agree to use contraception as detailed in [Appendix 5](#) of this protocol during the treatment period and for at least 2 days after the last dose of study treatment and refrain from donating sperm during this period.

b. Female participants:

Only female participants of non childbearing potential (WONCBP) as defined in [Appendix 5](#): Contraceptive Guidance and Collection of Pregnancy Information are eligible to participate.

Informed Consent

6. Capable of giving signed informed consent as described in [Appendix 3](#) which includes compliance with the requirements and restrictions listed in the informed consent form (ICF) and in this protocol.

